6.3.2.2 Acute Migraine-specific Medication Days per Month

During the DBT and OLE Phases, subjects may record taking triptan, ergotamine, and other medications to treat headache or during aura in the eDiary headache report.

Acute migraine-specific medication days per month are assessed as "acute migraine-specific medication days per 4 weeks" to correspond with the 4-week visit schedule. Acute migraine-specific medication days per month are based on 4-week interval, and are prorated to account for missing migraine reports. See Section 9.2.4 for the definition of acute migraine-specific medication day.

Acute Migraine-specific Medication Days per Month in the DBT Phase

Analyses are based on the DBT migraine analysis set with eDiary efficacy dates in the on-DBT efficacy analysis period.

The number of acute migraine-specific medication days per month in the DBT phase is prorated to 28 days and derived as follows:

- Month (i.e., 4-week interval) in the on-DBT efficacy analysis period: 28 × (total number of acute migraine-specific medication days in the month)/(total number of efficacy data days in the month). Subjects must have ≥ 14 days of efficacy data (not necessarily consecutive) in the specified month to be evaluable.
- Overall DBT: 28 × (total number of acute migraine-specific medication days through Month 3 in the on DBT efficacy analysis period)/(total number of efficacy data days through Month 3 in the on DBT efficacy analysis period).

Descriptive Analyses

The table of the number of acute migraine-specific medication days per month in the DBT Phase is provided, and summarizes the parameter descriptively as a continuous variable (including 2-sided normal 95% CIs for mean) by treatment group in each month of the DBT Phase and overall DBT.

Treatment Group Comparisons

Treatment groups are compared using a linear mixed effects model with repeated measures and the following attributes:

- Variables: number of acute migraine-specific medication days per month as the dependent variable; treatment group, randomization stratum, month (i.e., Months 1 to 3 of the DBT Phase), and the month-by-treatment group interaction as fixed effects
- Covariance structure for repeated measures accounting for within-subject correlated errors: See Section 6.3.1.1.
- SE estimation method: See Section 6.3.1.1.

The table displays the following model estimates:

- LSM, SE, and 95% CI by month and overall DBT for each treatment group
- Difference in LSMs between treatment groups (rimegepant placebo), SE, 95% CI, and pvalue at each month and overall DBT. Results in the last 4 weeks support secondary objective #4, whereas results at other time points support exploratory objective #6.

Model estimates by randomization stratum (yes, no) are presented in the same table, using additional models that exclude randomization stratum as a fixed effect.

Subgroup Analyses

Subgroup analyses of the acute migraine-specific medication days will use the same linear mixed effects model specified above. The following model estimates will be reported by subgroup of historical chronic migraine according to ICHD 3rd edition (yes or no) (Section 4.3). P-values are presented only for descriptive purpose.

• LSM, SE, and 95% CI by month in the DBT Phase and overall DBT for each treatment group

• Difference in LSMs between treatment groups (rimegepant - placebo), SE, 95% CI, and p-value by month and overall DBT.

Acute Migraine-specific Medication Days per Month in the OLE Phase

Analyses are based on the OL rimegepant migraine analysis set with eDiary efficacy dates in the on-OL rimegepant efficacy analysis period.

The number of acute migraine-specific medication days per month in the OLE Phase is prorated to 28 days and derived as follows:

- Month (i.e., 4-week interval) in the on-OL rimegepant efficacy analysis period: 28 × (total number of acute migraine-specific medication days in the month)/(total number of efficacy data days in the month). Subjects must have ≥ 14 days of efficacy data (not necessarily consecutive) in the specified month to be evaluable.
- Overall OL rimegepant: 28 × (total number of acute migraine-specific medication days through Month 10 in the on-OL rimegepant efficacy analysis period)/(total number of efficacy data days through Month 10 in the on-OL rimegepant efficacy analysis period).

The table of the number of acute migraine-specific medication days per month in the OLE Phase is provided, and summarizes the parameter descriptively as a continuous variable (including 2-sided normal 95% CIs for mean) by treatment group/OL rimegepant and overall in each month of the OLE Phase and overall OL rimegepant.

Results support exploratory objective #7.

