 - DBT migraine: subjects in the DBT efficacy analysis set with ≥ 14 days of eDiary data (not necessarily consecutive) in both the OP and ≥ 1 month (4-week interval) during the DBT Phase (see Section 6.3.1.1). This analysis set is used to assess migraine days, headache days, acute migraine-specific medication days, and acute migraine medication days during the DBT Phase.
 - DBT first month migraine: subjects in the DBT efficacy analysis set with ≥ 24 days of eDiary efficacy data (not necessarily consecutive) in both the OP and in first month (4week interval) of the DBT Phase (see Section 6.3.3.1). This analysis set is used to assess migraine and headache days per week during the DBT Phase.
- OL rimegepant efficacy: subjects in the DBT efficacy analysis set who take ≥ 1 dose of OL rimegepant. This analysis set is used to assess outcomes research endpoints during the OLE Phase.
 - OL rimegepant migraine: subjects in both the DBT migraine and OL rimegepant efficacy analysis sets with ≥ 14 days of eDiary efficacy data (not necessarily consecutive) in ≥ 1 month (4-week interval) in the OLE Phase. This analysis set is used to assess migraine days, headache days, acute migraine-specific medication days, and acute migraine medication days during the OLE Phase.

See Section 7.1 for derived dates and Section 7.2 for analysis periods.

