5 SAMPLE SIZE, POWER, AND TYPE I ERROR

The study randomizes approximately 245 subjects per treatment arm to obtain roughly 225 evaluable subjects per treatment arm.

With a sample size of roughly 490 subjects randomized, and 245 subjects per group, we expect roughly 225 evaluable subjects per group in the efficacy data set. Assuming rimegepant provides roughly a 1 day advantage over placebo on the primary endpoint, a common standard deviation of 3.75 days, and a 2-sided alpha level of 0.05, then the study will have roughly 80% power on the primary endpoint. The estimates for the change in migraine days per month and the standard deviation are consistent with publicly available information from another investigational oral CGRP antagonist for this indication.

Type I error will be controlled by using a hierarchical gate keeping procedure. If the primary endpoint is significant at the 2-sided alpha level of 0.05, then secondary efficacy or outcomes research endpoints are tested hierarchically, each at a 2-sided alpha level of 0.05, in the order in which they appear in Section 3.2.2. Thus, a secondary efficacy or outcomes research endpoint is tested only if the preceding secondary endpoint in the hierarchy is determined to be significant (i.e., p-value ≤ 0.05). If a test in the hierarchy is not significant, then any further tests on endpoints in the sequence have p-values presented only for descriptive purposes, and no conclusions are drawn from those results. Note that secondary safety endpoints are not tested.

For exploratory endpoints, no attempt is made to adjust for multiplicity. Any exploratory endpoints for which p-values are produced are evaluated at an unadjusted, 2-sided alpha level of 0.05 and presented only for descriptive purposes.

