6.2.5.2 Baseline Disease Characteristics

Migraine History

Refer to the Core SAP for the table of migraine history. The table also displays the following categorical variables:

- Experienced migraines for ≥ 1 year prior to screening (yes, no)
- Prophylactic migraine medications taken (yes, no).

Efficacy during the OP

The table of efficacy endpoints per month during the OP is provided only for the DBT migraine analysis set, and summarizes the following efficacy parameters descriptively as continuous or categorical variables during the OP analysis period:

- Migraine days per month by pain intensity (total; moderate or severe). Categories are < 6, ≥ 6, < 8, ≥ 8, < 12, ≥ 12, < 15, ≥ 15.
- Headache days per month by headache pain intensity (total; moderate or severe). Categories are same as for migraine days per month above.

- Acute migraine-specific medication days per month. Categories are 0, > 0 to < 2, ≥ 2 to < 4, ≥ 4.
- Acute migraine medication days per month. Categories are the same as for acute migraine-specific medication days per month above.

The table of efficacy endpoints per week during the OP is provided only for the DBT first month migraine analysis set, and summarizes the following efficacy parameters descriptively as continuous or categorical variables during the OP analysis period:

- Migraine days per week by headache pain intensity (total; moderate or severe). Categories are < 1, ≥ 1 to < 2, ≥ 2 to < 3, ≥ 3.
- Headache days per week by headache pain intensity (total; moderate or severe). Categories are same as for migraine days per week above.

See Sections 6.3.1 for migraine days per month, Section 6.3.2.2 for acute migraine-specific medication days per month, Section 6.3.3.3 for migraine days per week, Section 6.3.3.4 for acute migraine medication days per month, and Section 7.2 for the OP analysis period.

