6.3.1 Reduction in Migraine Days per Month

Subjects are instructed to report headache occurrence, headache pain features and associated symptoms, aura occurrence, and medication used to treat headache or aura in the eDiary headache report every day in the OP, DBT, and OLE Phases.

Migraine days per month are assessed as "migraine days per 4 weeks" to correspond with the 4week visit schedule. Migraine days per month are based on 4-week intervals, and are prorated to account for missing migraine reports.

See Section 9.2.2 for the definition of eDiary efficacy data days, and Section 9.2.5 for the definition of migraine days.

6.3.1.1 Reduction in Migraine Days per Month in the DBT Phase: Primary Efficacy Endpoint

The number of migraine days per month in the DBT phase is examined relative to the number of migraine days per month in the OP for the DBT migraine analysis set, i.e., subjects with ≥ 14 days of eDiary efficacy data (not necessarily consecutive) in both the OP analysis period and ≥ 1 month (i.e., 4-week interval) in the on-DBT efficacy analysis period.

Months in the DBT phase are defined as follows:

- Month 1 (\leq 4 weeks; study days 1 to 28)
- Month 2 (> 4 to \leq 8 weeks; study days 29 to 56)
- Month 3 (> 8 to \leq 12 weeks; study days 57 to 84).

Analyses are based on eDiary efficacy dates in the OP and on-DBT efficacy analysis periods.

The number of migraine days per month is prorated to 28 days and derived as follows:

- OP: 28 × (total number of migraine days in the OP analysis period)/(total number of efficacy data days in the OP analysis period). Subjects must have ≥ 14 days of eDiary efficacy data (not necessarily consecutive) in the OP to be evaluable.
- Month (i.e., 4-week interval) in the on-DBT efficacy analysis period: 28 × (total number of migraine days in the month)/(total number of efficacy data days in the month). Subjects must have ≥ 14 days of efficacy data (not necessarily consecutive) in the specified month to be evaluable.
- Overall DBT: 28 × (total number of migraine days through Month 3 in the on-DBT efficacy analysis period)/(total number of efficacy data days through Month 3 in the on-DBT efficacy analysis period).

Missing Efficacy Data

The frequency table of missing efficacy data in the OP and DBT Phase is provided for the DBT efficacy analysis set, and displays the following categories:

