- Included in the DBT migraine analysis set: ≥ 14 days of eDiary efficacy data (not necessarily consecutive) in both the OP and ≥ 1 month (i.e., 4-week interval) of the DBT Phase
 - Month 1: \leq 4 weeks *
 - Month 2: > 4 to ≤ 8 weeks *
 - Month 3: > 8 to ≤ 12 weeks *
- Excluded from the DBT migraine analysis set
 - \circ < 14 days of eDiary efficacy data in the OP
 - < 14 days of eDiary efficacy data in all 3 months of the DBT Phase.

In the categories marked with "*", subjects must have ≥ 14 days of efficacy data (not necessarily consecutive) in the specified month to be evaluable.

Descriptive Analyses

The table of values and changes (both absolute and percent) from the OP in the number of migraine days per month in the DBT Phase is provided for the DBT migraine analysis set, and summarizes parameters descriptively as continuous variables (including 2-sided normal 95% CIs for mean change) by treatment group and by pain intensity in each month of the DBT Phase and overall DBT. Pain intensity categories are (1) total (mild, moderate, severe, none, or not reported) and (2) moderate or severe. The table also presents results by subgroup level for all efficacy subgroups of interest described in Section 4.3.

In the percent change analyses, subjects must also have ≥ 1 migraine day (i.e., absolute not prorated to 28 days) of appropriate migraine severity in the OP analysis period to be included.

Treatment Group Comparisons

Analyses are based on DBT migraine analysis set and total pain intensity, unless otherwise specified.

Main Analysis: DBT Migraine Analysis Set

The main analysis of the primary endpoint uses a linear mixed effects model with repeated measures and the following attributes:

- Variables: change from the OP in number of total migraine days per month as the dependent variable; number of total migraine days per month in the OP as a covariate; treatment group, randomization stratum, month (i.e., Months 1 to 3 of the DBT Phase), and the month-by-treatment group interaction as fixed effects.

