6.3.2.3 Overall Summary of Primary and Secondary Endpoints in Hierarchical Testing

The overall summary table of treatment comparisons of all primary and secondary endpoints tested hierarchically displays the following statistics:

- Continuous endpoints involving change from OP or baseline
 - n (i.e., number of subjects in the analysis set), overall LSM change and 95% CI for each treatment group
 - Difference in overall LSM changes between treatment groups (rimegepant placebo), 95% CI, and p-value.

This applies to the primary endpoint and the following secondary efficacy and outcomes endpoints: mean change in the number of migraine days per month in the overall DBT Phase (see main analysis in Section 6.3.1.1); mean change in the number of migraine days per month in the first month of the DBT Phase (see main analysis in Section 6.3.1.1); MSQoL restrictive role domain score change from baseline at Week 12 (see Section 6.5.1); MIDAS total score change from baseline at Week 12 (see Section 6.5.2); and EQ-5D-5L VAS score change from baseline at Week 12 (see Section 6.5.3).

• Continuous endpoints not involving change from OP or baseline

- $\circ~$ n, overall LSM and 95% CI for each treatment group
- Difference in overall LSMs between treatment groups (rimegepant placebo), 95% CI, and p-value.

This applies to the secondary efficacy endpoint of the mean number of acute migraine-specific medication days per month in the last month of the DBT Phase (see Section 6.3.2.2).

- Binary endpoints
 - Response rate ("n/N") and 95% CI for each treatment group
 - Stratified percentage difference between treatment groups (rimegepant placebo), 95% CI, and p-value.

This applies to the secondary efficacy endpoint of the percentage of subjects with $\geq 50\%$ reduction in the mean number of moderate or severe migraine days per month in the last month of the DBT Phase (see Section 6.3.2.1).

Endpoints are displayed in the order presented in Sections 3.2.1 and 3.2.2. P-values that are determined to be significant based on the testing hierarchy are flagged.

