6.5.1 MSQoL

The MSQoL consists of 14 items across the following 3 domains: (1) restrictive role function, (2) preventative role function and (3) emotional function.

Descriptive Analyses

The table of values and changes from baseline in scores is provided by treatment group and overall for each domain for the DBT efficacy analysis set at the following time points: baseline; Week 12 of the DBT outcomes research analysis period; Week 24 and Week 52 in the OL rimegepant outcomes research analysis period. Results for overall are displayed only at baseline and time points in the OL rimegepant outcomes research analysis period. Results support exploratory objective #8.

The frequency table of MSQoL domain score reduction from baseline categories is provided by treatment group and overall for the DBT efficacy analysis set at the following time points: Week 12 of the DBT outcomes research analysis period; Week 24 and Week 52 in the OL rimegepant outcomes research analysis period. Results for overall are displayed only at time points in the OL rimegepant outcomes research analysis period.

Treatment Group Comparisons

Analyses of each domain are based on the DBT efficacy analysis set with paired data, i.e., nonmissing domain scores at both baseline and Week 12 of the DBT outcomes research analysis period.

For each domain, treatment groups are compared using a linear regression model with the following attributes:

- Variables: Week 12 change from baseline in the score as the dependent variable; baseline score as a covariate; treatment group and randomization stratum as fixed effects.
- SE estimation method: See Section 6.3.1.1..

The table provides n (i.e., number of subjects with paired data) and the following model estimates for each domain:

- LSM change from baseline at Week 12, SE, and 95% CI for each treatment group
- Difference in LSM changes from baseline at Week 12 between each rimegepant treatment group and placebo (rimegepant placebo), SE, 95% CI, and p-value.

Results for the restrictive role function support secondary objective #5, whereas results for the other domains support exploratory objective #8.

See Section 9.3.2 for example SAS code. Model estimates by randomization stratum (yes, no) are presented in the same table, using additional linear regression models that exclude randomization stratum as a fixed effect.

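### The SAP model for secondary endpoint 4 (acute migraine-specific medication days) omits the observation-period value as a covariate, so a test that gates three others loses avoidable precision

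*SAP*

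**What the plan says.** This point concerns the supplied SAP only, which is for the prevention study C4951021. The supplied protocol is for the acute-treatment study C4951022 and has no such endpoint.

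- **The model.** Section 6.3.2.2 specifies "number of acute migraine-specific medication days per month as the dependent variable; treatment group, randomization stratum, month" and the month-by-treatment interaction. Covariance structure and SE method are taken from 6.3.1.1 by cross-reference, but the variables are listed in full. The outcome is the on-treatment value; section 6.3.2.3 files it under "Continuous endpoints not involving change from OP or baseline".
- **The OP data.** Section 6.3.1 has subjects report "medication used to treat headache or aura in the eDiary headache report every day in the OP, DBT, and OLE Phases". Section 4.1 admits a subject to the DBT migraine analysis set only with at least 14 "days of eDiary data (not necessarily consecutive) in both the OP and" at least one DBT month. Section 6.2.5.2 says "The table of efficacy endpoints per month during the OP is provided only for the DBT migraine analysis set", and acute migraine-specific medication days per month is one of the parameters in that table.
- **The other continuous endpoints.** The primary model, which also serves secondary endpoints 2 and 3, has the "number of total migraine days per month in the OP as a covariate". The MSQoL model has the "baseline score as a covariate; treatment group and randomization stratum as fixed effects", and MIDAS and EQ-5D-5L VAS reuse it.
- **The sequence.** Under section 5, "a secondary efficacy or outcomes research endpoint is tested only if the preceding secondary endpoint in the hierarchy is determined to be significant". Endpoint 4 comes directly before MSQoL, MIDAS and EQ-5D-5L VAS.

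**The concern.** Subjects differ in how often they take triptans or ergotamine before treatment; the SAP's own OP categories run from 0 to 4 or more days per month. If that habit carries over into the treatment phase, the part the OP value would explain stays in the error term. The randomization stratum does not stand in for it, because it records stable prophylactic medication, not acute medication.

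The SAP gives no reason for treating endpoint 4 differently from the other six. Its definition as an on-treatment value is not a reason. In a linear model that contains the OP value as a covariate, analysing the value or the change from OP gives the same treatment coefficient. Under randomization, adding the covariate leaves the quantity being estimated unchanged.

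At stake is the chance of passing endpoint 4 and, through the fixed sequence, the right to test the three outcomes research endpoints after it. The exploratory model for acute migraine medication days in 6.3.3.4 copies the same terms and the same omission.

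**Working it through.** **Inputs from SAP section 5:** about 225 evaluable subjects per arm; two-sided alpha 0.05; for the primary endpoint only, a 1-day difference, SD 3.75 and roughly 80% power. For endpoint 4 the SAP gives no SD, effect size, power or OP correlation.

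**The SAP's own figure.** SE = 3.75 × √(2/225) = 0.354 and 1/0.354 = 2.83, so power = Φ(2.83 − 1.96) = 80.7%. The stated figure reproduces.

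**Effect of the covariate.** Let r be the correlation between the OP value and the on-treatment value given stratum (assumed).

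- Residual variance is multiplied by 1 − r², and the SE by √(1 − r²).
- The unadjusted test with 225 per arm is worth an adjusted test with 225 × (1 − r²) per arm.
- Adjusted power = Φ((z + 1.96)/√(1 − r²) − 1.96), where z is the normal quantile of the unadjusted power (also assumed).

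| r (assumed) | Variance reduction | SE reduction | Equivalent n per arm | Power from 50% | Power from 70% | Power from 80% |
|---|---|---|---|---|---|---|
| 0.3 | 9% | 5% | 205 | 53.8% | 74.0% | 83.6% |
| 0.5 | 25% | 13% | 169 | 61.9% | 81.8% | 89.9% |
| 0.7 | 49% | 29% | 115 | 78.4% | 93.6% | 97.5% |

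Worked case, r = 0.5 from 50%: z = 0, √0.75 = 0.866, 1.96/0.866 − 1.96 = 0.303, Φ(0.303) = 61.9%.

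**Simulation checks.** Both used 225 per arm, one month, stratum in the model and a robust SE.

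- *Normal data, 6000 runs per setting.* With no effect, rejection was 4.8–5.4% with either model. Adjusted-to-unadjusted variance ratios were 0.90–0.92, 0.72–0.77 and 0.50–0.51 for r = 0.3, 0.5 and 0.7, against 0.91, 0.75 and 0.51 from the formula.
- *Overdispersed day counts, 1500 runs per setting.* With no effect and r about 0.40, rejection was 4.9% unadjusted and 5.1% adjusted. With an effect and r about 0.70, the mean estimates agreed (−0.524 and −0.522 days), the mean SE fell from 0.265 to 0.192, and power rose from 51% to 77%.

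**The case against.** The strongest reply is that nothing here is an error. The unadjusted model is valid and pre-specified, and endpoint 4 is the only continuous endpoint in the sequence not defined as a change. SAP Version 2 revised this section's model and left the terms alone. The documents give no correlation, so they cannot show that the loss matters: from a starting power of 90%, r = 0.3 adds only about 2.5 points (to 92.5%). The factor 1 − r² is also a best case. The planned analysis is a three-month model, and a single OP slope common to all months gives the full reduction at Month 3 only if that slope fits Month 3. Endpoint 4 is itself reached only after the primary and secondary endpoints 1 to 3 succeed, so the powers above are not probabilities of losing the later endpoints.

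Much of this stands as a limit on size. The point is about efficiency, and both r and the starting powers are assumptions. It does not remove the point:

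- The value-versus-change distinction gives no ground for leaving the covariate out.
- The revision history for 6.3.2.2 refers to the changes made for the primary analysis and records no decision about this covariate.
- A common slope costs only the squared mismatch. With both variables scaled to SD 1, the Month 3 residual variance is 1 − r² + (b − r)² for a common slope b. At r = 0.5 and b = 0.6 that is 0.76 instead of 0.75.

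**Conclusion.** The concern holds. The SAP leaves the OP value out of the model for secondary endpoint 4, although that value can be derived for every subject analysed and the other six continuous endpoints in the sequence use theirs. The consequence is lost precision, with no bias and no inflation of type I error. The loss is small if r is near 0.3 and substantial if r is 0.5 or more; which applies cannot be settled from the documents. The change is recommended because it costs almost nothing and the test gates three others. The omission itself is plain from the text; only its size is uncertain.

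**What to change.** In SAP 6.3.2.2, add OP acute migraine-specific medication days per month as a covariate, in the same way that the primary model carries OP migraine days. Write out the derivation there: 28 × (acute migraine-specific medication days in the OP)/(efficacy data days in the OP). Section 6.2.5.2 refers to 6.3.2.2 for this parameter, but 6.3.2.2 has formulas for the DBT and OLE Phases only. The endpoint remains an on-treatment value. The by-stratum and chronic-migraine subgroup models should carry the same term. In 6.3.3.4, add OP acute migraine medication days likewise.

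One minor wording note: section 6.3.3.1 changes only the dependent variable for headache days, so read literally it keeps OP migraine days as the covariate. Naming OP headache days there would settle it. Those analyses are descriptive and the likely loss is modest.

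The cost is one model term and one formula, repeated in the dependent analyses, with no new data and no subject lost. The amendment must be dated before the PCD database lock, until which section 2.3 keeps the study blinded. The C4951021 protocol and the Core SAP were not supplied; if that protocol spells out this model, it would need the same change.
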